## **3 STUDY OBJECTIVE AND ASSESSMENTS**

### **3.1 Study Objective**

The objective of this study is to assess the long-term safety and tolerability of pimavanserin for the treatment of PDP.

### **3.2 Clinical Rating Scales**

The Caregiver Burden Scale, Clinical Global Impression-Severity (CGI-S), Clinical Global Impression-Improvement (CGI-I), and Unified Parkinson's Disease Rating Scale (UPDRS; a safety measure) parts II and III will be administered at all scheduled post-baseline visits. The Scale for the Assessment of Positive Symptoms (SAPS) will be administered at Month 1 only.

The Non-Motor Symptom scale (NMSS; a safety measure) for PD was initially collected in this study but was discontinued with amendment 6. Results will be presented in a data listing but will not be summarized.

The Resource Utilization in Dementia (RUD)-Lite (health economics outcome measure) will be collected at baseline (all subjects had a baseline RUD-Lite performed), Month 12, every 6 months thereafter, and at end of study.

### **3.3 Safety and Pharmacokinetic Endpoints**

The safety and pharmacokinetic assessments include the following:

- AEs;
- Physical examinations (PEs);
- Vital signs and body weight;
- ECGs;
- Clinical Laboratory including clinical chemistry, hematology, and urinalysis;
- Pimavanserin plasma concentrations (trough).

## **4 ANALYSIS SETS**

All analyses will be performed on the safety analysis set, which is defined as: all enrolled subjects who receive at least one dose of study drug (pimavanserin).

## **5 STATISTICAL CONSIDERATIONS**

### **5.1 General Statistical Procedures**

Statistical summaries will be generated using SAS® software, version 9.3 or higher. No formal statistical tests will be conducted. Unless otherwise specified, continuous parameters will be summarized using the following descriptive statistics: number of observations, mean, median, standard deviation (SD), standard error of the mean (SEM), minimum and maximum. Categorical parameters will be summarized using the number and percentage of subjects in each level of a category.

Descriptive statistics will be presented using a significant figure rule: the minimum and maximum will have the same number of significant figures as the data; the mean and median will have one more significant figure than the data being summarized; the SD and SEM will have two more significant figures than the data being summarized; and the sample size (n) will be reported as an integer.

Unless otherwise indicated, descriptive statistics will be reported for observed cases only and missing data will not be imputed. Missing observations will not be taken into account when calculating frequencies, unless otherwise indicated. By-visit summary tables will include all available subjects' data up to 4 years (192 weeks) on study, and any data beyond that point will be summarized in a single visit (>192 weeks). For laboratory, vitals, and ECGs by time period summaries an additional last assessment will be included.

Data listings will include all data for all subjects. Listings will present data sorted by site number, subject identification, study day, and visit (both nominal and derived, if applicable), unless otherwise specified. If a listing includes a derived visit, then in those cases where a subject has more than one result in the derived visit window the result that is used for analysis will be flagged in the listing.

### **5.2 Multiplicity Issues**

Multiplicity is not an issue because there are no formal statistical analyses.

### **5.3 Coding Dictionary**

Adverse events will be coded using the Medical Dictionary for Regulatory Activities (MedDRA, version 15.1). Prior and concomitant medications will be coded using the March 2013 version of the World Health Organization (WHO) Drug Dictionary.

### **5.4 Analysis Visit Window, Time Periods and Missing Values**

#### **5.4.1 Visit Windows for Clinical Rating Scales**

For clinical rating scales (e.g. SAPS associated scores, CGI associated scores and CBS) measured between first dose date and last dose date + 3, data will be summarized using the derived visit based on the visit windows shown in [Table 1](#).

Nominal visits as specified in [Appendix A](#) will be re-assigned to the derived visits. The re-assigned visit will be referred to as the ‘derived visit’ as identified in Table 1 below. After reassignment of a visit, if there are multiple assessments for the same visit, the assessment nearest to the target study day will be kept for analysis. In the event of a tie, the assessment from the earlier study day will be kept for analysis. Unscheduled visits are included in the visit re-assignment.

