1.2 Previous Clinical Experience

ACADIA has initiated 17 clinical trials of pimavanserin. Fifteen of these studies are completed and 2 studies are ongoing (Study ACP-103-010 and Study ACP-103-015). Of the 15 completed studies, 14 have been analyzed; analysis is ongoing for the other study (ACP-103-014). The 2 ongoing studies, Study ACP-103-010 and Study ACP-103-015, are open-label safety trials. A total of 882 subjects have had exposure to pimavanserin. Of these subjects, 447 were PD/PDP patients, 258 were healthy volunteers and 177 were schizophrenic patients. In a long-term, open-label safety trial in PDP patients (Study ACP-103-010), 23 subjects have received pimavanserin for > 12 months, including 13 subjects treated for ≥ 24 months and 2 subjects treated for > 60 months. As of May 1st, 2010, both those subjects remain active.

In the other long-term, open-label safety trial in PDP subjects (ACP-103-015), 77 subjects have received pimavanserin for > 12 months and 6 subjects have received pimavanserin for > 24 months. As of May 1st, 2010, 160 subjects remain active.

All studies have been, or are being, conducted in accordance with Good Clinical Practice, the ethical principles that have their origin in the Declaration of Helsinki, and applicable local regulatory requirements.

Across study populations (healthy volunteers as well as patients), pimavanserin has been shown to be generally safe and well tolerated at single doses up to 300 mg and multiple doses up to 160 mg. The most common adverse events (AEs) were similar in healthy normal volunteers, PD patients, and schizophrenia patients and occurred at a similar frequency between pimavanserin- and placebo-treated subjects. The majority of AEs reported in studies to date were considered mild to moderate in nature.

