## **5.12 Interim Analyses and Data Safety Monitoring Board**

To provide an adequate update of the long-term safety profile for pimavanserin's new drug application (NDA) submission, a data snapshot was taken on 13DEC2013 and an interim analysis will be performed.

There is no Data Safety Monitoring Board (DSMB) for this study. Safety data are monitored throughout the study and aggregate safety reports are produced and reviewed approximately quarterly.

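### The open-ended >Week 192 derived visit keeps one rating per subject, nearest Day 1513, so for CGI and Caregiver Burden it mainly shows Week 216

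*SAP*

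**What the plan says.** SAP 5.4.1 sets the scope of the windowing: "For clinical rating scales (e.g. SAPS associated scores, CGI associated scores and CBS) measured between first dose date and last dose date + 3". Within a derived visit, "if there are multiple assessments for the same visit, the assessment nearest to the target study day will be kept for analysis", and "In the event of a tie, the assessment from the earlier study day will be kept for analysis". Unscheduled visits are windowed too. No exception is made for the last row.

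In SAP Table 1 the six-monthly rows from Week 72 to Week 192 are closed. The last row, >Week 192, has target Day 1513 and starts at Day 1430 with no end.

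SAP 5.1 describes what that row is for. By-visit tables run to 192 weeks, and "any data beyond that point will be summarized in a single visit (>192 weeks". The same section keeps everything in the listings ("Data listings will include all data for all subjects") and adds a last-assessment summary for laboratory tests, vital signs and ECGs only.

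Protocol 3.1 and Table 1 schedule CGI-S, CGI-I and the Caregiver Burden Scale at every visit, every 168 days after Month 12, for as long as the subject stays in. SAP 5.11.2 to 5.11.4 summarise them by visit, overall and by geographic area.

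**The concern.** A nearest-to-target rule suits a window that holds one scheduled visit. The last window can hold many, and its target sits at the first of them. The choice is therefore systematic: among a subject's late ratings, the rule favours the earliest scheduled one.

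This is an open-ended extension with a long-term objective, and description is its only output. A reader who follows SAP 5.1 will take the >Week 192 row as the pooled experience beyond that point. A CGI or Caregiver Burden rating taken years later, including an end-of-study rating within three days of the last dose, does not enter the row if the subject was also rated around Week 216. The scores of the longest-treated subjects at their longest exposure would then be missing from the by-visit tables, and nothing in the row's label would show it.

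**Working it through.** **1. The plan's own target.** Table 1 targets follow target day = 7 × week + 1. For Week 192 this gives 7 × 192 + 1 = 1345, as printed. Inverting for the last row gives (1513 − 1) / 7 = Week 216.

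**2. The closed rows.** The Week 192 window is 1262–1429, with width 1429 − 1262 + 1 = 168 days. It extends 1345 − 1262 = 83 days below target and 1429 − 1345 = 84 days above. The rows from Week 72 on have the same shape. The same shape around Day 1513 would be 1430–1597.

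**3. What the rule selects in the open row.** Distance is |day − 1513|.

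- Day 1430: 83
- Day 1597: 84
- Day 1598: 85

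Any rating in Days 1430–1597 therefore beats any rating from Day 1598 on. For a subject with at least one rating in that interval, the open row returns exactly what a closed Week 216 row would return.

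**4. Scheduled visits.** Visit days are 336 + 168k. Those at or after Day 1430 are below.

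| Followed to | Visit day | Distance from 1513 | Kept | Ratings left out of the row |
|---|---|---|---|---|
| Week 216 | 1512 | 1 | 1512 | 0 of 1 |
| Week 240 | 1680 | 167 | 1512 | 1 of 2 |
| Week 264 | 1848 | 335 | 1512 | 2 of 3 |
| Week 288 | 2016 | 503 | 1512 | 3 of 4 |
| Week 312 | 2184 | 671 | 1512 | 4 of 5 |

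**5. Exceptions.** A subject with no rating near Day 1513 contributes another: if Day 1512 is missed, Day 1680 is kept. A subject whose only in-window rating is on Day 1440 contributes that one.

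**6. Sensitivity to attendance (assumed; not in the documents).** Take four scheduled visits to Week 288, each attended independently with probability p. Among subjects in the row, the share represented by Week 216 is p / (1 − (1 − p)^4). The share of in-window ratings left out is 1 − (1 − (1 − p)^4) / (4p).

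| p | Row from Week 216 | Ratings left out |
|---|---|---|
| 1.00 | 100% | 75% |
| 0.95 | 95% | 74% |
| 0.90 | 90% | 72% |
| 0.80 | 80% | 69% |

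**7. Could anyone be this far out?** Protocol 1.2 reports, at 1 May 2010, that "77 subjects have received pimavanserin for > 12 months and 6 subjects have received pimavanserin for > 24 months". SAP 5.12 says "a data snapshot was taken on 13DEC2013". The gap is 1096 days (to 1 May 2013) + 226 = 1322 days. Reading 12 and 24 months as 365 and 730 days, a subject just past those marks who was still on drug at the snapshot would be at about Day 365 + 1322 = 1687 and Day 730 + 1322 = 2052. The first is just past the second in-window visit (Day 1680) and the second is past the fourth (Day 2016). So late ratings are possible at the snapshot, and more so at the final report.

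**The case against.** The strongest reply is that little is at stake. The objective is safety, no tests are planned, the rows to Week 192 are intact, and pooling a sparse tail is normal practice. Nearest-to-target also keeps the time point comparable across subjects, whereas a last value mixes durations. SAP 5.1 itself foresees a single value per window, since if "a subject has more than one result in the derived visit window the result that is used for analysis will be flagged in the listing". All of this is fair, and it limits the weight of the point. It does not rescue the row: one value per subject is a reasonable choice, but the plan should not then describe the row as holding the data beyond Week 192.

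Some stronger readings are tempting, and the documents do not support them:

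- *That all later ratings are dropped, or that the row is Week 216 only.* The ratings stay in the listings, and subjects without a rating near Day 1513 contribute an earlier or later one.
- *That late worsening cannot appear in any summary table.* Withdrawal reasons by period, including the sponsor's re-classified category for lack of efficacy or progression of psychosis (SAP 5.5), adverse events by onset period (SAP 5.13.1) and UPDRS worst and last values (SAP 5.13.6) all extend past Day 1462. What is missing is the late CGI and Caregiver Burden scores.
- *That 77 and 6 subjects are affected.* Protocol 1.2 says how long they had received drug. It does not say that they were still active on 1 May 2010, or that they stayed to the snapshot.
- *That equating 4 years with 192 weeks in SAP 5.1 is an error.* The visit calendar puts Month 12 at Day 336, and 4 × 336 = 1344 = 192 × 7, so the phrase fits that calendar.

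**Conclusion.** The point holds as a mismatch between a row's description and its content. Followed as written, SAP 5.4.1 makes the >Week 192 row a Week 216 row for every subject rated in Days 1430–1597. With on-schedule attendance the by-visit tables omit from half (follow-up to Week 240) to three quarters (to Week 288) of that subject's in-window CGI-S, CGI-I and Caregiver Burden ratings, and the share grows with follow-up. At assumed attendance of 80–100% per visit over four visits, about 80–100% of the row still comes from Week 216.

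The number of subjects affected cannot be derived, because retention is not given. SAPS (Month 1 only) and UPDRS (summarised by the Table 2 periods) are untouched. The effect is on how very-long-term status is described; no test or inference is involved. It is worth correcting because the correction is cheap.

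**What to change.** Continue Table 1 in closed windows of the same shape as the existing ones:

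| Derived visit | Target day | Range |
|---|---|---|
| Week 216 | 1513 | 1430–1597 |
| Week 240 | 1681 | 1598–1765 |
| Week 264 | 1849 | 1766–1933 |

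and so on in 168-day steps to the last visit observed. Amend the sentence in SAP 5.1 to match.

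If a single pooled row is preferred, label the present row as approximately Week 216, and add a last on-treatment assessment row for CGI-S, CGI-I (with responders) and Caregiver Burden, parallel to the one already planned for laboratory tests, vital signs and ECGs. Because that row mixes durations, show the spread of study days beside it.

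The cost is SAP wording, a small programming change and a few table rows whose late entries will have small n. No new data are needed.

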3. STUDY DESIGN

3.1 Overall Study Design

Pimavanserin will be administered once daily at a fixed dose level of 40 mg. The study will be conducted on an outpatient basis.

Subjects who have completed the treatment period of a previous blinded study of pimavanserin in PDP subjects and who may, in the opinion of the Investigator, benefit from continued treatment with pimavanserin will be enrolled in this study for safety evaluation. Subjects may be enrolled in this study as early as the last visit of the treatment phase of the previous study OR up to 28 days following completion of the treatment period.

Subjects will be required to visit the clinic on Week 2 (Day 14 ± 3 days), Month 1 (Day 28 ± 3 days), Month 3 (Day 84 ± 7 days), Month 6 (168 days ± 7 days), Month 9 (252 days ± 7 days), Month 12 (336 days ± 7 days) and every six months thereafter (every 168 days ± 7 days). Unscheduled clinical evaluations may occur at anytime if deemed appropriate by the Investigator. If the subject terminates the study at any time other than a planned visit the subject will be required to visit the clinic for an end-of-study evaluation.

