3.6.2.5. End-of-Study Visit

Subjects may be removed from this trial at anytime. Upon termination of the subjects' enrollment in this study an End-of-Study visit will be scheduled and the following procedures will be conducted:

- Weight
- 12-Lead ECG
- Vital Signs
- Physical Examination
- Clinical Laboratory Tests

- Serum Pregnancy Test, if applicable
- Plasma collection for pimavanserin determination
- Caregiver Burden Scale
- UPDRS Parts II and III
- CGI-S and CGI-I
- Follow Up RUD Lite (only for subjects with a Baseline RUD Lite assessment at the Baseline Visit)
- Adverse events
- Concomitant Medications

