## **5.5 Subject Enrollment and Disposition**

Subject enrollment by protocol amendments and subject counts by study center and prior study will be summarized.

A summary of subject disposition will display the number of subjects enrolled, received study drug, and remained in the study (using visit dates recorded on the vital signs CRF) at the beginning of the following time periods: first 4 weeks (Study Days 1 to 28), 1 to 3 months (Study Days 29 to 91), >3 to 6 months (Study Days 92 to 183), >6 month to 1 year (Study Days 184 to 365), >1 to 2 years (Study Days 366 to 730), >2 to 3 years (Study Days 731 to 1095), >3 to 4 years (Study Days 1096 to 1461) and >4 years (Study Days >=1462). Also included in this summary will be subject discontinuations showing the number of subjects who terminated from the study according to the reason for study termination/discontinuation (Investigator reported and Sponsor re-classified). Reasons for study termination will also be summarized by the time period specified above.

The withdrawal reasons as reported by the investigators on the eCRF are:

- Adverse event
- Death
- Disease progression
- Subject's voluntary withdrawal of consent (Voluntary withdrawal of consent)
- The Investigator determines that continuation in the study would be detrimental to a subject's well-being because of development of a serious illness, any other significant change in clinical status, or any other compelling medical reason (Investigator decision)
- Subject fails to comply with protocol requirements (Subject non-compliance)
- Lost to follow-up
- At discretion of Sponsor (Sponsor decision)

To better understand the discontinuation pattern, ACADIA reviewed the withdrawal reasons and in some cases, on the basis of verbatim comments in the eCRF, re-classified the reasons for discontinuation using the following categories:

- Adverse event
- Death
- Lack of efficacy / PDP progression
- PD /Concomitant disease progression
- Voluntary withdrawal of consent
- PDP improvement
- Investigator decision
- Subject non-compliance
- Lost to follow-up
- Sponsor decision

Subject disposition and study completion by Investigator-specified and Sponsor-reclassified reasons for termination will be presented in data listings and summary tables. Dispositions will also be summarized by 3 regions: North America (US and Canada), Europe and India.

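### The by-visit CGI and Caregiver Burden summaries can leave out the score taken at withdrawal, and unlike the other repeated measures these scales have no last-assessment summary

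*SAP*

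**What the plan says.** Protocol 3.6.2.5 states that when a subject's participation ends "an End-of-Study visit will be scheduled and the following procedures will be conducted". The list includes the Caregiver Burden Scale (CBS), CGI-S and CGI-I. Under Protocol 3.1 a separate end-of-study evaluation is needed only when the subject stops at a time other than a planned visit.

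SAP 5.4.1 takes rating-scale data "measured between first dose date and last dose date + 3" and places them in the Table 1 windows. Where a window holds several scores, "the assessment nearest to the target study day will be kept for analysis"; if two are equally near, the earlier one is used. Visits off the schedule are covered too: "Unscheduled visits are included in the visit re-assignment". No separate rule is given for End-of-Study visits.

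SAP 5.11.2 to 5.11.4 summarise CBS, CGI-S and CGI-I (including responders) by visit only, overall and by geographic area. SAP 5.1 says: "For laboratory, vitals, and ECGs by time period summaries an additional last assessment will be included". A last value is also planned in SAP 5.13.3 (laboratory), 5.13.4.1 (vital signs), 5.13.4.3 (weight and BMI), 5.13.5.1 (ECG) and 5.13.6 (UPDRS). None is planned for CGI or CBS.

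SAP 5.1 keeps every score in the listings and flags the analysed one. SAP 5.5 tabulates reasons for stopping, including the sponsor's category "Lack of efficacy / PDP progression".

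**The concern.** SAPS is given only at Month 1, so from then on CGI is the only summarised rating of psychosis. The by-visit CGI-I responder percentage will be read as the long-term course of response, in a study where treatment continues only while it is thought to help.

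A subject who stops between planned visits may have two scores in the final window: the scheduled one and the one at stopping. The rule favours the scheduled score whenever stopping comes later in the window. The subject then has no data in the next window, and SAP 5.1 specifies observed cases without imputation. The status recorded at stopping thus enters no summary table for these scales. For laboratory values, vital signs, weight, ECG and UPDRS, the last-value summary guards against this kind of loss.

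**Working it through.** The documents state no discard rate, so there is no figure to reproduce. The inputs are the Table 1 windows and targets, the selection and tie rules in SAP 5.4.1, and the visit schedule in Protocol 3.1. The distribution of withdrawal times, and the lag from last dose to the End-of-Study visit, are assumptions.

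**1. The rule applied to two invented cases.** The scheduled visit is on Day 169 in both.
- End-of-Study on Day 200: both scores fall in Week 24 (Days 127–210). The distances from target are 0 and 31, so Day 169 is kept and Day 200 is left out. Week 36 starts on Day 211 and has no score from this subject.
- End-of-Study on Day 230: this falls in Week 36 (Days 211–294) as the only score there, and is kept.

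**2. Days affected, by window.** With the scheduled score on its target day, an End-of-Study score is left out on every later day of the window. Days affected = upper bound − target.

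| Window | Target | Days in window | Days affected |
|---|---|---|---|
| Week 2 | 15 | 20 | 21 − 15 = 6 |
| Week 4 | 29 | 21 | 42 − 29 = 13 |
| Weeks 12, 24, 36 | 85, 169, 253 | 84 each | 41 each |
| Week 48 | 337 | 127 | 421 − 337 = 84 |
| Weeks 72 to 192 (six windows) | 505 to 1345 | 168 each | 84 each |

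Affected: 6 + 13 + 3×41 + 84 + 6×84 = 730. Total: 20 + 21 + 3×84 + 127 + 6×168 = 1428. Share: 730/1428 = 51.1%.

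Removing the 12 scheduled-visit days, on which no extra visit arises, gives 730/1416 = 51.6%. With the three-monthly visits used before Amendment 6 it is 723/1409 = 51.3%. Week 48 is the worst window, at 84/126 = 67% of off-schedule days, because it runs 84 days past its target but only 42 days before it.

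**3. Other withdrawal patterns.** These were simulated with visits varying by ±3 or ±7 days and the End-of-Study visit on the last dose day. Withdrawals after Day 2200 were not counted. Ranges cover the schedules before and after Amendment 6.

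| Median of exponential withdrawal time | Share left out | Share left out if 25% stop at a planned visit |
|---|---|---|
| 90 days | 38% | 29% |
| 183 days | 42–43% | 32–33% |
| 365 days | 47% | 35–36% |
| 548 days | 50% | 37–38% |
| 730 days | 52–53% | 39–40% |

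**4. The limit of last dose plus three days.** This acts before the nearest-to-target rule. If the lag is equally likely to be 0 to 7 days, lags of 4 to 7 are excluded: 4/8 = 50%. In the same simulation the window rule removes another 19–26%, for a total of 68–77%. With a lag of 0 to 14 days the limit alone removes 11/15 = 73%, and the total is 83–87%.

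**5. After Week 192.** The last window is Day 1430 onward with target 1513, and one score per subject is kept. The scheduled visit at Day 336 + 7×168 = 1512, within ±7 days, lies at most 8 days from target (1513 − 1505). If it was attended, any End-of-Study score from Day 1521 on is left out, since 1521 − 1513 = 8 is at best a tie and ties go to the earlier day.

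**The case against.** The strongest reply is that this is a safety study. Protocol 12.2 plans no formal analysis of these scales and promises only descriptive statistics at each visit, which the SAP delivers. On that view, giving last values to the safety measures and not to CGI or CBS is a presentation choice. This stands as a limit on severity: the primary objective is untouched. It does not remove the gap, because the tables will be produced and read.

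Three stronger readings might be inferred, and the documents do not support them.
- *Half of all withdrawn subjects lose their final score.* The 51% counts calendar days, not subjects. It assumes uniform off-schedule withdrawal and an attended scheduled visit in the window. Protocol 4.2 asks for every effort to complete the End-of-Study procedures but stops data collection, apart from ongoing adverse events, once consent is withdrawn. Death and loss to follow-up would normally yield no score. The share applies only to End-of-Study scores actually obtained.
- *Deterioration disappears.* Roughly half of in-range off-schedule scores stay in the by-visit tables, and all stay in the listings. Stopping reasons are tabulated overall and by period (SAP 5.5), exposure is summarised by reclassified reason (5.7.1), adverse events leading to discontinuation by period (5.13.1, 5.13.2), and post-treatment antipsychotics separately (5.9.2). These do not correct a visit mean or responder percentage, but worsening is not hidden from the report.
- *Long-term response is shown to be biased upward.* The rule ignores the value of the score, and the reclassified reasons also include improvement of the psychosis. The direction depends on who stops and why, which the documents do not give. Any drift from subjects leaving follows mainly from observed-case summaries, which this point does not change.

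**Conclusion.** The point holds in a limited form. The nearest-to-target rule, applied without an exemption for End-of-Study visits, usually leaves out an off-schedule End-of-Study CGI or CBS score that follows an attended scheduled visit in the same window. No last-assessment summary recovers it.

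For End-of-Study visits within three days of the last dose, the share is about 51% of off-schedule days under uniform withdrawal, 38–53% under the exponential patterns tried, and 29–40% if a quarter of subjects stop at a planned visit. Missed scheduled visits would lower it. The three-day limit adds to the loss by an amount that depends on an unstated lag.

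The by-visit means and CGI-I responder percentages can therefore under-represent status at withdrawal. That is a reason for a small addition to a descriptive analysis. It does not establish a bias of known direction.

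**What to change.** In SAP 5.11.2 to 5.11.4 add a last on-treatment assessment row for CGI-S, CGI-I (values and responders) and CBS. Use each subject's last post-baseline score up to last dose plus three days, whatever its window. Leave the by-visit tables as they are. This matches the SAP's practice for laboratory values, vital signs, weight, ECG and UPDRS, and brings the loss of in-range End-of-Study scores to the nearest-to-target rule down to zero in that row.

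The cost is one extra row per table from data already collected, with no protocol change. The row mixes different treatment durations, so it must be labelled that way and not read as a further time point. Scores later than last dose plus three days would still be outside it. If they are shown, present them separately as off-treatment, for example in a listing, because they may reflect stopping the drug or a replacement antipsychotic.
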